This is a multi-site, cluster-randomized clinical trial supported by the infrastructure of the Palliative Care Research Cooperative Group (PCRC). It is a parallel randomization trial with a wait-list control, randomizing nephrologists within each site to receive the intervention at study initiation or after study completion. We will enroll a total of 320 pre-dialysis patients with an estimated glomerular filtration rate (eGFR) of less than 20mL/min/1.73M² who are age 60 and older and have an estimated survival of 18 months or less.³⁶ We expect eight sites are required to ensure complete enrollment (one enrollment plan for example, 8 sites x 4 nephrologists per site with 10 patients per nephrologist = 320). (Note: two sites were added in 2022, for a total of ten sites.) We will follow patients for up to two years after study enrollment. At the start of the study, within each site, nephrologists are randomized to the control or intervention group in a ratio of 1:1. A block randomization scheme will be utilized with blinded block size. Nephrologists assigned to the intervention group will receive training on how to use the Best Case/Worst Case communication tool. Patients in the control group will receive usual care; patients in the intervention group will receive care from their nephrologist trained to use the Best Case/Worst Case communication tool. Palliative care will be available to all patients.

Table: Outcomes Measures for Each Aim				
Construct	Specific Measure	Type; range	Source	Timing
Aim 1: receipt of palliative care and intensity of treatments received at the end of life				
Receipt of palliative care	Any palliative care consult within 12 months of enrollment	Binary; 0/1	Chart review	T0 to 12 mo
Intensity of treatment	ICU admission within 30 days of death	Binary; 0/1	Chart review	T3 minus 30d.
Aim 2: Health-related Quality of Life				
Health related quality of life	Functional Assessment of Chronic Illness Therapy-Palliative Care Version 4 (FACIT-Pal)	Continuous; 0-184	Patient	T2a.... T2h
Aim 3: Quality of Communication				
Quality of Communication	Quality of Communication Questionnaire (QOC)	Continuous; 0-10	Patient	T1
Secondary Outcomes and Follow-up Measures				
Receipt of palliative care	Receipt of any palliative care during study period Hospice enrollment New documentation of advance care planning	Binary; 0/1 Binary; 0/1 Binary; 0/1	Chart review Chart review Chart review	T0 to 2 yr. T0 to 2 yr. T0 to 2 yr.

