Data and Safety Monitoring Plan

No formal interim analyses are planned during this study, and all study outcomes will be assessed at the completion of study follow-up.

Meetings of the DSMB will be held at least two times a year at the call of the Chairperson. DSMB interim report templates will be prepared by a study statistician with assistance from the PCRC and the Data, Informatics and Statistics Core (DISC), to be reviewed by the DSMB members at the first meeting.

Analysis of Primary Outcome

The sample size estimate, 320 patients (160/group), is based on the primary hypothesis that patients in the intervention arm will be more likely to receive palliative care and will have fewer intensive treatments at the end of life. We aim to recruit 32 nephrologists, each treating on average 10 study patients. We estimate a 10% attrition rate for study participation and that 80% of patients will die during the 2-year study period. This study is powered to detect a 10-15% absolute difference in the care patients receive, consistent with other interventions designed to effectively increase access to palliative care.³⁷⁻⁴⁰

Smaller differences are unlikely to be considered meaningful to clinicians, patients or researchers.⁴¹ We desire a two-sided type I error rate of 0.05 and estimate that the between-physician variance is around 10%. We plan to use fixed effects to account for clustering by site because it is faithful to our study design and controls for confounding related to imperfect randomization due to site imbalances better than a random effects model. Assuming the baseline rate of palliative care is 10%,^{42,43} we will have a power of 90% to detect a 14.7% increase and a power of 80% to detect a 12.9% increase in the rate of palliative care received.

General Analysis Plan

Primary Outcome

1. For receipt of **palliative care consult within 12 months of study enrollment**, for each treatment arm, we will report the sample counts and percentages. The denominator for each proportion will include all randomized subjects to the respective treatment arm. The treatment effect will be assessed using a Likelihood Ratio Test (LRT) of the fixed effect from the proportional odds cumulative incidence model, incorporating the competing risk of death.⁴⁴ The model will include a random-intercept for physician, and will include fixed effects for: site, comorbidity, and baseline functional status.

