19. For **caregiver-reported end-of-life Quality of Communication (QOC)** within 48 hours of enrollment, for each treatment arm, we will report the mean and standard deviation of the general 7-item subscale composite scores. The treatment effect will be assessed using a LRT of the fixed effect from the linear mixed-effects model. The linear mixed-effects model will include a random-intercept for physician, and will include fixed effects for: site, comorbidity, and baseline functional status.

Null Hypothesis: After accounting for baseline differences, there is no difference in average end-of-life QOC scores between control patients and Best Case/Worst Case intervention patients.

Alternative Hypothesis: After accounting for baseline differences, there is a difference in average end-of-life QOC scores between control patients and Best Case/Worst Case intervention patients.

Exploratory analyses

1. Per-protocol analysis:

The study team will assess adherence to the Best Case/Worst Case intervention using ascertainment and review of the Best Case/Worst Case graphic aid. Primary outcomes for aims 1 through 3 will be repeated removing those in the intervention group that did not adhere to the protocol, specifically removing those who did not receive the Best Case/Worst Case intervention.

2. Heterogeneity of Treatment Effect (HTE):

To determine the impact of the intervention on different subgroups of interest, heterogeneity of treatment effects will be explored. Mixed-effects models with random-intercepts for nephrologist will be fit for each primary outcome in Aim 1 to 3. These models will be fit with a fixed-effect interaction term between intervention status and the following subgroup variables: gender, race/ethnicity (minority/non-minority), health literacy (low/high), age (less than 80/older than 80), insurance status (Medicaid (dual eligible)/no Medicaid), and nephrologist background (MD/advance practice provider (PA/NP)). Significance in interaction fixed-effects will indicate heterogeneity of treatment effect. Caregiver outcomes (secondary analysis outcomes 9-12) will also be explored for HTE in a similar manner.

3. Casual Mediation Analysis:

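### The exploratory treatment-by-age interaction is tested only as a split at 80, which loses information if the effect changes gradually with age

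*SAP*

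**What the plan says.** Item 2 under Exploratory analyses in the SAP (Heterogeneity of Treatment Effect) covers the main outcome of each of Aims 1 to 3, using mixed models with a random intercept for nephrologist. On the interaction it says: "These models will be fit with a fixed-effect interaction term between intervention status and the following subgroup variables". Age is one of six variables listed and is coded "age (less than 80/older than 80". The reading rule is "Significance in interaction fixed-effects will indicate heterogeneity of treatment effect". The aim is stated modestly: "heterogeneity of treatment effects will be explored".

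No interaction with age in years is planned, no reason is given for cutting at 80, and no power is stated for any interaction. The only information on age is the entry criterion under Study design, which takes patients "who are age 60 and older and have an estimated survival of 18 months or less". No mean, standard deviation or expected share above 80 appears.

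**The concern.** The lower age group can span 20 years. A patient of 61 and one of 79 are treated as alike, while one of 79 and one of 81 are treated as different. If the benefit of the communication tool rises or falls gradually with age, a two-level variable captures only part of that gradient. The test then has less power than the same patients could give, and any difference found is attributed to a boundary at 80 that may have no special meaning.

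At stake is the reading of an exploratory result. The SAP identifies heterogeneity by the significance of the interaction term, so a real gradient is more likely to go unnoticed. The coding also has a small gap: a patient aged exactly 80 is in neither group.

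**Working it through.** **1. The plan's own power figures.** The SAP gives none for the age interaction, so only the main effect can be reproduced. The inputs, from Analysis of Primary Outcome, are:

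- "The sample size estimate, 320 patients (160/group" and "We aim to recruit 32 nephrologists, each treating on average 10 study patients"
- "We estimate a 10% attrition rate for study participation"
- a 10% control rate, two-sided 0.05, and a between-physician variance of about 10%
- stated power of 90% for a rise of 14.7 points and 80% for a rise of 12.9 points

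The scale of that variance is not stated. I assume 0.10 on the logit scale, which gives an intracluster correlation of about 0.009 in control and 0.018 in intervention. After attrition there are 160 × 0.9 = 144 per arm and 10 × 0.9 = 9 per nephrologist. With design effect 1 + (9 − 1) × ICC, power is about 88% for 10% versus 24.7% and about 80% for 10% versus 22.9%. Both are within 2 points of the SAP.

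**2. Information kept by the split, normal ages.** If the effect is linear in age, the share of information kept is the squared correlation between age and the above/below indicator. With a share p above the cut and z the matching normal quantile, this is φ(z)² / [p(1 − p)].

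| Share above 80 (assumed) | φ(z) | Kept | Lost |
|---|---|---|---|
| 50% | 0.399 | 0.159/0.25 = 0.64 | 36% |
| 40% | 0.386 | 0.149/0.24 = 0.62 | 38% |
| 30% | 0.348 | 0.121/0.21 = 0.58 | 42% |
| 20% | 0.280 | 0.078/0.16 = 0.49 | 51% |

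**3. Other assumed distributions.** Entry at 60 cuts off the lower tail, so normality is itself uncertain.

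- Uniform ages: the share kept is 3p(1 − p). For 60 to 100, p = 0.5 and the loss is 1 − 0.75 = 25%. For 60 to 95, p = 15/35 and the loss is 1 − 0.735 = 27%.
- Normal truncated at 60, underlying mean 74 to 78, SD 8: loss 43% down to 36%.
- Normal truncated at 60, underlying mean 70 to 82, SD 6 to 10: loss from about 33% to about 75%. The largest value is for mean 70 and SD 6, where only 5% are 80 or over.
- A true step at 80: no loss.

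**4. Power of the split test.** This uses receipt of palliative care on the risk-difference scale, ignores clustering, and takes a control rate of 10% in both age groups. The average effect is 14.7 points and the interaction is also 14.7 points. With a share q aged 80 or over, the effect is 14.7 + (1 − q) × 14.7 points in the older group and 14.7 − q × 14.7 points in the younger. For q = 0.5 and 160 per arm, the intervention rates are 0.3205 and 0.1735, and

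SE = √[(0.09 + 0.09 + 0.3205 × 0.6795 + 0.1735 × 0.8265)/80] = 0.0822.

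Power = Φ(0.147/0.0822 − 1.96) = 43%. The interaction detectable with 80% power is about 2.80 × 0.0822 = 23 points.

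| Share 80 or over | Power, 160/arm | Power, 144/arm | Detectable at 80% power, 160/arm | Detectable at 80% power, 144/arm |
|---|---|---|---|---|
| 50% | 43% | 40% | 23 points | 24 points |
| 20% | 27% | 25% | 31 points | 33 points |

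**5. What continuous age would recover.** If the split loses a fraction L, its noncentrality (1.96 plus the normal quantile of its power) is divided by √(1 − L) when continuous age is used. For example, with 30% power and L = 0.40: (1.96 − 0.524)/√0.60 = 1.853, and Φ(1.853 − 1.96) = 46%.

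| Power on the split | L = 25% | L = 40% | L = 50% |
|---|---|---|---|
| 20% | 25% | 30% | 35% |
| 30% | 38% | 46% | 53% |
| 50% | 62% | 72% | 79% |

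**The case against.** The strongest defence is that the SAP asks about subgroups, and a cut fixed in advance with a formal interaction test is conventional and prevents a data-driven choice of cut-point. The background uses ages 80 to 85 as its example of poor survival after starting dialysis, so 80 is a recognisable boundary in this document. If the effect does change there, the split is the better model and a linear term the wrong one. The analysis is exploratory.

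The exploratory status stands and limits the importance of the point. The possibility of a step also stands, and it makes the loss conditional. The rest does not remove the point. The background example is not offered as a reason for the cut. A continuous-age test can be fixed in advance just as firmly and needs no cut-point. The subgroup estimates can still be shown.

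A reader might infer three stronger things that the SAP does not support:

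- **A single figure, such as 40% of the information lost.** That lies mid-range under some assumptions, but the SAP supplies no age distribution and no shape for the effect.
- **That the split equals discarding the same share of the 320 patients.** The ICU outcome uses only patients who died (80% expected, so about 256 of 320 before attrition). Patients are also clustered by nephrologist, and the formula is only approximate for binary outcomes.
- **That low interaction power breaks a promise.** The SAP claims no power for this test.

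**Conclusion.** The point holds as a modest, conditional improvement. The age interaction is tested only as an unexplained split at 80. Under a roughly linear gradient the loss is about 36% to 51% for normal ages with 50% to 20% above the cut, and about 25% to 75% across a wider set of assumed distributions. It is nil if the effect steps at 80. The age distributions and the linear gradient are assumptions, not facts from the SAP.

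Power for an interaction the size of the main effect is about 25% to 43% on the split, from an approximation that ignores clustering. A non-significant split would therefore say little about whether the effect varies with age. The SAP does not say that it would read such a result as uniformity of effect. The primary analysis is unaffected.

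**What to change.** In item 2 of the Exploratory analyses:

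- Test treatment by age in years, with the matching main effect of age, in the same mixed models.
- Add a spline or quadratic term as a check on linearity.
- Report the estimated treatment effect with its interval at several ages, such as 65, 75 and 85.
- Keep the split at 80 for display only, coded under 80 and 80 and over, so that age exactly 80 is assigned.

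The cost is a change of SAP wording, with no new data. The downside is that the main test assumes an approximately linear gradient on the model's scale, which is why the linearity check and the displayed subgroup estimates should stay.
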